4.4.10 Annualized joint bleeding rate

The annualized joint bleeding rate (AJBR) will be summarized descriptively by age cohort and overall as described in Section 4.4.1.

4.4.11 Target joint resolution

Participants will be assessed for target joints at screening by the investigator. A target joint is defined as a major joint (eg, hip, elbow, wrist, shoulder, knee or ankle) into which \geq 3 spontaneous bleeding episodes occurred in a consecutive 6-month period. Resolution is achieved when \leq 2 bleeds occur into that joint during 12 months of continuous exposure (1).

The percentage of participants with resolution of at least 1 target joint and the percentage of total target joints that are resolved at 52 weeks will be summarized per age cohort and overall. Determination of resolution will be based on the number of spontaneous bleeding episodes into that joint as well as based on the number of total bleeding episodes into that joint (regardless of type). In this analysis, only participants who have at least 12 months of exposure (defined as duration of dosing \geq 52 weeks) to BIVV001 will be included. Target joints on which surgery was performed on or before the end of the participant's 12 months of exposure will be censored.

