1.3 SCHEDULE OF ACTIVITIES (SOA)

Table 1 - Overall schedule of activities from screening to safety follow-up call or visit

Tests and assessments	Screening ^{a, b} (Week -8 to Day 1)	Baseline ^b BIVV001 Day 1	Week 4 ^c ±7 days	Week 13 ^c ±7 days	Week 26 ^c ±7 days	Week 39 ^c ±7days	Week 52 ±7 days EOS/ET ^c	Unscheduled visit ^d	Safety follow- up call or visit ^e
Informed consent ^f	X								
Assessment of eligibility	X	X							
Demographics ^g	X								
Weight	X	X	X	X	X	X	X		
Height	X				X		X		
Medical, surgical, and hemophilia history ^h	X								
FVIII activity (1-stage aPTT assay) ^j	X								
Genotype ⁱ				X					
In-clinic BIVV001 dosing ^k		X	X	X	X	X	X		
Safety									
Physical exam	X	X	X		X		X	X	
Vital signs ^l	X	X	X		X		X	X	
HIV, HBV, and HCV status ^m	X								
CD4 count, viral load ⁿ	X								
Hematology ^o	X	X	X	X	X	X	X		
Coagulation parameters ^p		X			X		X		
Clinical chemistry ^q	X	X	X	X	X	X	X		

Tests and assessments	Screening ^{a, b} (Week -8 to Day 1)	Baseline ^b BIVV001 Day 1	Week 4 ^c ±7 days	Week 13 ^c ±7 days	Week 26 ^c ±7 days	Week 39 ^c ±7days	Week 52 ±7 days EOS/ET ^c	Unscheduled visit ^d	Safety follow- up call or visit ^e
von Willebrand Comprehensive Panel ^f		X	X	X	X	X	X		
Nijmegen-modified Bethesda assay (inhibitor assay) ^j	X	X	X	X	X	X	X		
Anti-rFVIII-Fc-VWF-XTEN Antibody (ADA) ^j	X	X	X	X	X	X	X		
Adverse event/serious adverse event recording ^s	<<ongoing; monitor and record at all visits>>								
Prior and concomitant medications and concomitant therapies and procedures ^t	<<ongoing; monitor and record at all visits>>								
Monthly telephone call ^u	<<ongoing; once per month, after Week 4>>								
Efficacy									
HJHS joint assessments (≥4 years old) ^v		X			X		X		
Investigator's target joint assessment		X							
Physician's global assessment of response to treatment (PGA)				X			X		
Investigator's assessment of participant's response to treatment of bleeding episodes at the study site ^w		<<ongoing>>							
Left-over serum and plasma samples material preserved for future research ^x (optional)	X	X	X	X	X	X	X		
Electronic patient diary (ePD) training/administration/review ^y	X	X	<<ongoing>>						

Tests and assessments	Screening ^{a, b} (Week -8 to Day 1)	Baseline ^b BIVV001 Day 1	Week 4 ^c ±7 days	Week 13 ^c ±7 days	Week 26 ^c ±7 days	Week 39 ^c ±7days	Week 52 ±7 days EOS/ET ^c	Unscheduled visit ^d	Safety follow-up call or visit ^e

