7.1 DISCONTINUATION OF STUDY INTERVENTION

7.1.1 Definitive discontinuation

Participants who discontinue study drug for any reason should have every effort made to conduct the assessments at the EOS/ET visit as specified in the SoA ([Table 1](#)).

The Investigator, Sponsor, or designee may discontinue dosing in a participant if the participant:

- Is in significant violation of the protocol
- Is non-adherent to treatment regimen
- Experiences a serious or intolerable AE
- Requires a prohibited medication

A participant must permanently discontinue study treatment if any of the following occur:

- Participant develops an inhibitor (see [Section 8.3.7](#) for definition of inhibitor development)
- Participant experiences a Grade 3 or greater allergic reaction per Common Terminology Criteria for Adverse Events (CTCAE) version 5.0 or an anaphylactic reaction in association with BIVV001 administration
- The participant or his caregivers withdraws consent

The Investigator may confer with the Sponsor or Study Medical Manager before discontinuing dosing in the participant.

Participants or their caregivers may decide that IMP be discontinued.

If a participant discontinues dosing due to an AE or SAE, the event should be followed as described in [Section 8.3.3](#). When a participant discontinues IMP dosing, the primary reason must be recorded in the appropriate section of the eCRF.

See the SoA ([Table 1](#)) for data to be collected at the time of study drug discontinuation and follow-up, and for any further evaluations that need to be completed.

Handling of participants after definitive intervention discontinuation

Participants will be followed-up according to the study procedures specified in this protocol up to the scheduled date of study completion, or up to recovery or stabilization of any AE to be followed-up as specified in this protocol, whichever comes last.

If possible, and after the definitive discontinuation of study drug, the participants will be assessed using the procedures in the ET/EOS visits. All participants should also complete the Safety Follow-up Call or Visit, refer to [Section 1.3](#).

All cases of definitive study drug discontinuation must be recorded by the Investigator in the appropriate pages of the e-CRF when considered as confirmed.

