4.1.1 Definition of study periods

This section defines the study periods used for different analyses, including treatment period, efficacy period, surgical/rehabilitation period, and safety period.

All analyses and summaries relating to bleeding and consumption will be based on the *efficacy period* (Section 4.1.1.2); data collected during the PK and surgical/rehabilitation periods (major and minor) will not be included.

All other efficacy analyses will be based on the *treatment period* (Section 4.1.1.1), excluding data that occurs during any major surgical/rehabilitation period to avoid confounding the treatment effect. Analysis of efficacy endpoints that are visit-based will not include visits that are coincidental with a major surgical/rehabilitation period.

Surgical evaluations will be based on the *surgical/rehabilitation period* (Section 4.1.1.3).

All safety analyses will be based on the *safety period* (Section 4.1.1.4). Unless otherwise specified, adverse events and laboratory evaluations occurred during major surgical/rehabilitation periods will not be included in the safety summaries.

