4.1.1.1 Treatment period

The treatment period is defined as the actual treatment that the participant follows.

The start date and time of the treatment period is defined as the date and time of the first dose of study drug (or, if the time is not available, at 00:01 on the day of the first dose). The end date and time of the treatment period is defined as 23:59 on the day of the last dose of study drug.

The duration of treatment period is the time period from the start of the treatment period to the end of that treatment period. The total duration will be calculated in minutes and converted to days as the number of minutes divided by 1440.

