4.1.1.2 Efficacy period

The efficacy period will be used for the evaluation of bleeding and consumption endpoints. For a participant to have an evaluable efficacy period over the duration of study, he/she must have at least 2 prophylactic dose of study drugs. The efficacy period is defined as the treatment period interrupted for PK periods, surgical/rehabilitation periods (major and minor) and large injection intervals as described below.

Adjustments Due to PK sampling period(s)

For participants undergoing PK sampling after their first dose of BIVV001, the efficacy period starts with the date and time of the first prophylactic dose following the completed PK sampling period (168 hours), and ends with the end of the treatment period as defined in Section 4.1.1.1. That is, if the initial PK sampling period is incomplete due to an aborted collection of blood samples following the PK injection (eg, because of a bleeding episode that required treatment), then the efficacy period will begin following a subsequent fully executed PK sampling period.

Adjustments Due to Surgical/Rehabilitation Periods

For analysis purposes, the efficacy period will be adjusted for all surgical/rehabilitation periods (major and minor). The start and end of the efficacy period are adjusted as follows:

- For all participants, the efficacy period continues up to 1 minute before the start of a surgical/rehabilitation period.
- For participants on a prophylactic regimen following the end of a surgical/rehabilitation period, the efficacy period for the prophylactic regimen re-starts at the first prophylactic dose following the end of the surgical/rehabilitation period.

Statistical Analysis Plan BIVV001-EFC16295 23-Aug-2021 Version number: 1

Bleeding episodes that occur during the surgical/rehabilitation period will be attributed to the surgical/rehabilitation period and hence not counted towards the ABR.

Adjustments Due to Large Injection Intervals

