4.7.1.1 Overall exposure

The extent of investigational medicinal product (IMP) exposure will be assessed by the number of injections and exposure days to BIVV001 and duration of BIVV001 dosing based on the Safety Analysis Set.

Number of Injections and Exposure Days to BIVV001

For any participant, the total number of days of exposure to BIVV001 will be accumulated from the time of their first on-study injection of BIVV001. An ED is a 24-hour period in which one or more BIVV001 injections are given. The 24-hour window starts from the first injection on study and then for subsequent injections, it starts from an injection taken after/outside of a previously identified ED.

The total number of EDs on BIVV001 for each participant will be summarized categorically (<5, 5-<10, 10-<25, 25-<50 and \geq 50; and \geq 1, \geq 5, \geq 10, \geq 25, \geq 50) and with descriptive statistics for the Safety Analysis Set.

The total number of injections per participant will be summarized overall and by reason for injection (prophylactic regimen, spontaneous bleed, traumatic bleed, follow-up injection, surgical or other) using descriptive statistics for the Safety Analysis Set.

Duration of BIVV001 Dosing

The duration of BIVV001 dosing will be calculated from the start date time of the treatment dose to the end date time, as defined in Section 4.1.1.1. Any interruptions to dosing will not be accounted for when calculating this duration.

Duration of BIVV001 dosing (weeks) will be summarized using descriptive statistics for the Safety Analysis Set. Weeks will be represented in the descriptive statistics as if these were data collected with 1 decimal place. The number and percentage of participants whose duration of dosing was at least 13, 26, 39, and 52 weeks will be summarized.

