When injections are identified in the ePD with exactly the same date/times, bleed information if applicable (type, location, and sublocation), lot numbers, number of vials, and vials strength in nominal IU, these may have resulted due to administrative issues and are therefore true duplicates. There are three types of administrative issues as follows:

- Technical transmission issue
- Entry of same record into 2 different devices
- Records duplicated in ePD and eCRF which remain despite attempts to correct the data via the query process

The programming algorithm to identify and delete the duplicates is as follows:

- Identify all injections that have exactly the same date/times, reasons for injection, bleed information (if applicable), lot numbers, number of vials, and vials strength in nominal IU
- Remove the duplicates and keep a single record

As with single vial consolidation, if injections identified as duplicates have distinctly different reasons (eg, one injection is recorded as bleeding or surgery and another is recorded as prophylaxis or OTHER), then these cannot be considered duplicates and removed. However, if one reason is missing, then they can be considered duplicates and removed.

Algorithm for determining analysis visit windows for PRO and HJHS observations

A scheduled measurement will be used if it is available. Otherwise, the following analysis window will decide how the unscheduled and EOS/ET visits will be used in the analyses of PRO and HJHS variables.

A measurement (unscheduled or EOS/ET) will be used if it is available and measurement date is within the analysis window.

After applying these time windows, if multiple assessments are associated to the same time point, the closest from the targeted study day will be used. If the difference is a tie, the value after the targeted study day will be used. If multiple valid values exist within a same day, then the first value of the day will be selected.

Scheduled visit post		Derived Window in study days		
baseline	Target study day	Lower bound	Upper bound	
Baseline	1	-INF	1(7 for HJHS)	
Week 26	182	2 (8 for HJHS)	272	
Week 52	364	273	-	

Table 6 - Analyses window definition

Handling of adverse events with missing or partial date/time of onset

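### Target-joint resolution: the 52-week dosing cut makes no allowance for the ±7-day Week 52 window, and eligibility and bleed counting run on different periods

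*SAP*

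**What the plan says.** SAP 4.4.11 calls a target joint resolved when no more than two bleeds occur in it over 12 months of continuous exposure. It then limits the analysis: "In this analysis, only participants who have at least 12 months of exposure (defined as duration of dosing" ≥52 weeks). It gives no visit-window tolerance and does not name the period in which bleeds are counted.

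Duration of dosing is set elsewhere. SAP 4.7.1.1 takes it from the start to the end of the treatment period and adds: "Any interruptions to dosing will not be accounted for when calculating this duration". SAP 4.1.1.1 starts that period at the first-dose time and closes it as follows: "The end date and time of the treatment period is defined as 23:59 on the day of the last dose of study drug". SAP 4.1 makes the first dose Day 1.

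The protocol's schedule of activities heads the final visit "Week 52 ±7 days EOS/ET" and includes an in-clinic dose. The only study day that the SAP gives for Week 52 is Day 364, in "Table 6 - Analyses window definition", which was written for PRO and HJHS data.

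For bleeding analyses SAP 4.1.1 prescribes the efficacy period, and "data collected during the PK and surgical/rehabilitation periods (major and minor) will not be included". If a first PK profile is aborted, "then the efficacy period will begin following a subsequent fully executed PK sampling period" (SAP 4.1.1.2). Protocol 9.4.3 likewise bases bleeding data on the efficacy period.

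**The concern.** This is a named secondary endpoint, and it covers only children who have a target joint at baseline, so one child can move the percentage.

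Two things are at stake. First, a child who followed the protocol can be dropped only because the last visit fell in the earlier part of its permitted window. Second, two clocks are in use. PK time counts towards the 52 weeks needed for eligibility, but bleeds in that time do not count against resolution. When a profile was aborted, the uncounted time is not a random stretch: it contains the treated bleed that stopped the sampling.

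**Working it through.** **Inputs.** Threshold 52 × 7 = 364 days (SAP 4.4.11), which equals the Week 52 target day in SAP Table 6. First dose = Day 1 (SAP 4.1). End of clock 23:59 on the last-dose day (SAP 4.1.1.1). Visit window ±7 days (Protocol Table 1). PK profile 168 h (SAP 4.1.1.2). Washout before a repeat profile 240 h (Protocol 10.7.4). PK subgroup 24 of about 65 children.

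**Step 1: duration of dosing.** For a last dose on Day D and a first dose at clock time t, duration = (D − 1) + (23:59 − t)/24 h. With a first dose assumed at 10:00:

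| Last dose | Days | Weeks | ≥364 days? |
|---|---|---|---|
| Day 357 | 356.58 | 50.94 | no |
| Day 358 | 357.58 | 51.08 | no |
| Day 364 | 363.58 | 51.94 | no |
| Day 365 | 364.58 | 52.08 | yes |

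The most favourable start, the imputed 00:01, gives 363.9986 days for Day 364, two minutes short. SAP 4.7.1.1 shows weeks to one decimal, but only for descriptive statistics. If the rounded value were tested instead, Day 364 would pass only with a first dose by about 08:23.

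**Step 2: permitted visit days.** Week 52 at Day 365 gives a window of Days 358–372, of which Days 358–364 fail (7 of 15). Week 52 at Day 364 gives Days 357–371, of which Days 357–364 fail (8 of 15).

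**Step 3: exact weekly dosing.** The 52nd dose falls on Day 1 + 51 × 7 = 358 and the 53rd on Day 1 + 52 × 7 = 365. The child passes, but only through the 53rd dose, at the Week 52 visit.

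**Step 4: counted time in the PK subgroup.** Starting from 364.58 days:
- One completed profile removes 7 days: 357.58 days = 51.08 weeks.
- An aborted profile removes 0–7 days to the bleed + 10 days of washout + 7 days of repeat profile = 17–24 days, leaving 49.65–48.65 weeks.

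**Step 5: effect on classification.** Assumption: Poisson bleeding into the joint at 1, 2, 3 or 4 per year (365.25 days). P(≤2 bleeds) over 364.58 days = 0.920, 0.678, 0.424, 0.239. Increase in percentage points from shorter counted time:

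| Days lost | 1/yr | 2/yr | 3/yr | 4/yr |
|---|---|---|---|---|
| 7 | 0.35 | 1.04 | 1.30 | 1.15 |
| 17 | 0.83 | 2.52 | 3.21 | 2.87 |
| 24 | 1.17 | 3.55 | 4.57 | 4.12 |

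**Step 6: the stopping bleed.** P(at least one bleed into the joint in 7 days) = 1.9%, 3.8%, 5.6%, 7.4%. If it happens, leaving that bleed out changes the classification with probability P(exactly 2 further bleeds in the counted time), about 17, 27, 24 and 16–17%. Even if all 24 PK children had a target joint, the expected number of changed classifications is 24 × the product of the two, taken rate by rate: about 0.08 to 0.32 of a child.

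**The case against.** Four points can be made for the plan.

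1. **The cut implements the definition.** Resolution requires 12 months of continuous exposure, and 364 days is already slightly under that. Relaxing it moves further away. This stands as a cost of the fix, and it is why the strict cut should be kept as a sensitivity analysis.

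2. **Table 6 is not a dosing schedule, and weekly dosing ends on Day 365.** Both are true. A reader might take 7 or 8 of 15 days to mean that about half the children are excluded. The documents do not support that: they give no distribution of last-dose days, and the share is zero on exact weekly dosing.

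3. **The counting period is not open.** A reader might infer from the silence of SAP 4.4.11 that nobody knows whether PK-period bleeds count. SAP 4.1.1 and Protocol 9.4.3 answer this: resolution is a count of bleeds, so the efficacy period applies. What survives is the mismatch with an eligibility clock that runs on the treatment period.

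4. **Little is lost.** The analyses are descriptive, and SAP 4.7.1.1 reports how many children reach 39 and 52 weeks of dosing. That shows the overall shortfall, but not which target joints it removes.

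A reader might also object that injection gaps over 28 days count towards the 52 weeks although they interrupt exposure. SAP 4.1.1.2 attributes such gaps to missing data, so the documents do not show that exposure stopped.

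**Conclusion.** The first part holds on the SAP's own definitions, with no assumption beyond testing unrounded values: a last dose on or before Day 364 is always excluded, although the visit and its dose are permitted then. How many children this removes cannot be computed, because the documents give neither the number of children with a target joint nor the spread of last-dose days.

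The second part holds as a mismatch of periods. Lost time after a normal PK profile is worth about 0.4–1.3 points in P(≤2 bleeds) under the Poisson assumption. The uncounted stopping bleed matters more to the child concerned, but it is rare enough that the expected effect is at most about 0.3 of a child. Its direction is always towards resolved. Both parts merit a wording change; neither threatens the endpoint as a whole.

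**What to change.** Both changes belong in SAP 4.4.11.

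(a) **Eligibility.** Include children whose last dose is on or after study Day 357 (Table 6's Day 364 minus 7), and keep the ≥52-week cut as a sensitivity analysis. Write the rule as a study day: a cut of 51 weeks (357 days) would still drop Day 357, which gives at most 356.9986 days. Keep it tied to dosing rather than to attendance, because Protocol 7.1.1 keeps children who stop treatment under observation: "Participants will be followed-up according to the study procedures specified in this protocol up to the scheduled date of study completion".

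Cost: up to about one week less observation for some children, a slight departure from 12 months. It raises P(≤2 bleeds) by about 0.4–1.3 points for 7 days, under Poisson bleeding at 1–4 per year. The extreme comparison, Day 357 against Day 365, is 8 days and gives 0.4–1.5 points by the formula in step 5.

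(b) **Counting period.** Name the efficacy period by cross-reference to SAP 4.1.1. Add a supplementary result that also counts treated target-joint bleeds during PK periods, including aborted profiles. Surgical/rehabilitation periods stay excluded and operated joints stay censored.

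Cost: one sentence and one extra result, labelled as supplementary because it steps outside the efficacy-period rule. The main analysis keeps to Protocol 9.4.3, and no new data are needed.

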8.1.6 Investigator's target joint assessment

The Investigator will assess target joints at Baseline according to the ISTH criteria. A target joint is defined as a major joint (eg, hip, elbow, wrist, shoulder, knee or ankle) into which ≥ 3 spontaneous bleeding episodes occurred in a consecutive 6-month period. Target joint resolution is defined as ≤ 2 bleeding episodes in the target joint over 12 months of continuous exposure.

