The percentage of participants with resolution of at least 1 target joint and the percentage of total target joints that are resolved at 52 weeks will be summarized. A target joint is defined as a major joint (eg, hip, elbow, wrist, shoulder, knee or ankle) into which ≥ 3 spontaneous bleeding episodes occurred in a consecutive 6-month period and resolution is achieved when ≤ 2 bleeding episodes occur into that joint during 12 months of continuous exposure.

The consumption of BIVV001 will be annualized and summarized.

The number of injections and total dose of BIVV001 to treat a bleeding episode will be summarized on both a per-bleeding-episode and a per participant basis, where the per-participant basis will be determined as the average over all bleeding episodes for a given participant.

The participant's response to treatment of individual bleeding episodes will be summarized as the number and percentage of bleeding episodes with each response (excellent, good, moderate, or none).

The physician's global assessment of the participant's overall response to BIVV001 treatment will be summarized for each study visit and across all visits as the number and percentage classified as excellent, effective, partially effective, and ineffective.

For Haem-A-QoL, total score and physical health domain score will be summarized descriptively over time.

Surgical endpoints will be summarized descriptively for the surgical subgroup. Continuous endpoints will be summarized using the number of non-missing values (n), mean, SD, median, minimum, and maximum. Categorical endpoints will be summarized by counts and percentages.

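### Target-joint resolution can be overstated, because joints already known to have failed leave the percentage if they are operated on or the child is dosed for under 52 weeks

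*SAP*

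**What the plan says.** Protocol 9.4.3 names two summaries: "The percentage of participants with resolution of at least 1 target joint and the percentage of total target joints that are resolved at 52 weeks". It adds that "resolution is achieved when ≤ 2 bleeding episodes occur into that joint during 12 months of continuous exposure". Protocol 8.1.6 gives the same definition, counting "bleeding episodes in the target joint over 12 months of continuous exposure".

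SAP 4.4.11 keeps both percentages ("the percentage of total target joints that are resolved at 52 weeks will be summarized per age cohort and overall") and adds three specifications:

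- **Exposure:** the analysis includes "only participants who have at least 12 months of exposure", defined as a duration of dosing of at least 52 weeks.
- **Surgery:** "Target joints on which surgery was performed on or before the end of the" child's 12 months are to be censored. The term is not defined further.
- **Two versions:** "Determination of resolution will be based on the number of spontaneous bleeding episodes into that joint", and separately on all bleeding episodes whatever their type.

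Neither the exposure rule nor the surgery rule makes an exception for a joint that has already bled three or more times. The protocol states neither exclusion explicitly. The planned sensitivity analyses (SAP section 3 and 4.4.1.3) concern the annualized bleeding rate only.

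**The concern.** A 12-month requirement is sensible for a joint with 0 to 2 bleeds and short follow-up, because its status at 12 months is unknown. A joint with a third bleed at Month 5 is different. It has failed the definition whatever happens later, and the diary already holds the evidence. SAP 4.4.11 treats both joints alike: if the child stops early or the joint is operated on, both leave the calculation.

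If joints that bleed more are more likely to leave, those remaining are a favourable selection and the percentage is too high. The documents make such a link plausible. Protocol 7.1.1 requires permanent discontinuation after an inhibitor, and caregivers may stop treatment at any time. Surgery on a joint that keeps bleeding is also plausible. This endpoint serves the joint-health objective, and no planned output shows how many excluded joints had already failed or why they left.

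**Working it through.** **Inputs.** From the documents: the limit of 2 bleeds in 12 months (Protocol 8.1.6 and 9.4.3), the two exclusions and the use of simple percentages (SAP 4.4.11), and about 65 enrolled to obtain at least 50 with 50 exposure days (SAP section 2). The number of target joints, the expected resolution rate and the number of exclusions are not given. The plan states no figure for this endpoint, so there is nothing to reproduce. Everything below is illustrative.

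**Step 1: effect of restoring known failures.** Let r be the resolved joints, n the joints kept by the SAP, and f the excluded joints that already had 3 or more bleeds. The SAP percentage is r/n. With known failures counted it is r/(n+f).

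| r/n | f = 0 | f = 1 | f = 2 |
|---|---|---|---|
| 4/5 | 80.0% | 4/6 = 66.7% | 4/7 = 57.1% |
| 9/10 | 90.0% | 9/11 = 81.8% | 9/12 = 75.0% |
| 18/20 | 90.0% | 18/21 = 85.7% | 18/22 = 81.8% |

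One known failure moves the figure by about 4 to 13 points when 5 to 20 joints are evaluable. With f = 0 nothing changes.

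**Step 2: comparison with the true rate.** Step 1 compares two estimators; it does not show which is closer to the truth. Time to third bleed was therefore simulated for 400,000 joints per setting, at true resolution of 60%, 80% and 90%. There were three exclusion mechanisms:

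- **A, unrelated:** 15/65 = 23% of joints excluded at a random time (Poisson bleeding).
- **B, rate-linked:** exclusion hazard proportional to the joint's bleeding rate, calibrated to 23% excluded (gamma-mixed Poisson bleeding).
- **C, after failure:** half of the joints with a third bleed before Month 12 excluded just after it (Poisson bleeding).

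| True | Mechanism | SAP percentage | Known failures counted | Kaplan-Meier |
|---|---|---|---|---|
| 60% | A | 60.0% | 57.6% | 60.0% |
| 60% | B | 68.2% | 62.3% | 64.2% |
| 60% | C | 75.0% | 60.1% | 60.1% |
| 80% | A | 80.1% | 78.6% | 80.0% |
| 80% | B | 86.0% | 82.5% | 83.7% |
| 80% | C | 88.9% | 80.0% | 80.0% |
| 90% | A | 90.0% | 89.2% | 90.0% |
| 90% | B | 93.7% | 91.9% | 92.5% |
| 90% | C | 94.8% | 90.0% | 90.0% |

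Under A the SAP percentage is unbiased, and counting known failures leans low: 80.0 − 78.6 = 1.4 points at a true 80%. Under B and C at a true 80% the SAP percentage is high by 86.0 − 80.0 = 6.0 and 88.9 − 80.0 = 8.9 points. Both alternatives are then closer to the truth, although neither removes the bias under B.

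**Step 3: bounds at a true 80%.** The worst case counts every excluded joint as not resolved. The best case adds back as resolved the excluded joints with unknown status: best = worst + (excluded − known failures).

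- A: worst 61.6%; best 61.6 + (23.0 − 1.5) = 83.1%.
- B: worst 66.2%; best 66.2 + (23.0 − 3.3) = 85.9%.
- C: worst 80.0%; best 80.0 + (10.0 − 10.0) = 80.0%.

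The bounds contain the true rate under all three mechanisms.

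**The case against.** **The 52-week cut follows the protocol.** The protocol defines resolution over 12 months of continuous exposure, so the cut puts that definition into practice. This stands. A reader might infer that the SAP departs from a protocol endpoint with no duration requirement, and the documents do not support that. On surgery, Protocol 8.1.7 already excludes bleeds and follow-up in surgical/rehabilitation periods, and Protocol 10.7.1 classes any operation on a joint as major surgery. Removing the whole joint, including bleeds before surgery, goes further and appears only in the SAP.

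**Exclusion may be unrelated to bleeding.** Under Protocol 4.4, ongoing participants are called in once the end-of-study milestone is met. Exclusion by that route leaves the SAP percentage unbiased (mechanism A). A reader might conclude that resolution *is* overstated in favour of BIVV001. The documents support only *can be*.

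**Size.** A reader might take the 15 of 65 children not counted on to reach 50 exposure days, let g be the share of their joints that had failed, and compare R/50 with R/(50 + 15g). The relative excess is 0.30g; a reported 90% becomes 90/1.075 = 83.7% at g = 25%. The arithmetic is right, but this is not an estimate of bias. Fifty exposure days is not the 52-week criterion, the enrolment figures are approximate, target joints need not be spread in proportion, g is unknown, and the comparator itself leans low under unrelated exclusion.

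**Simply counting known failures makes entry depend on outcome.** A failure could then enter at any time, while a success must complete 12 months. This stands, and is why that percentage should accompany the planned one and not replace it.

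**The bleeds are not lost.** Those in the efficacy period count in the annualized joint bleeding rate (SAP 4.4.10). Dosing duration, discontinuation reasons, surgeries and baseline target joints are also reported. What is missing is a joint-level account of who was excluded and which of those joints had failed.

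**Conclusion.** The point holds as a possibility, not as a demonstrated bias. SAP 4.4.11 lets known failures leave the denominator, and no planned analysis of this endpoint shows or corrects it. The percentage is too high only if exclusion is related to bleeding and some excluded joints had already reached a third bleed. The size cannot be derived from the documents. The 6 to 9 points at a true 80% rest on assumed mechanisms, and the 4 to 13 points per restored joint on assumed counts of 5 to 20 evaluable joints.

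The endpoint is secondary and descriptive, so no test or sample size is affected. This is a cheap improvement to make before database lock.

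**What to change.** In SAP 4.4.11, keep the 52-week definition and the planned percentages, and state that 'censored' means removed from those percentages. Then add the following, separately for the spontaneous-only and all-bleeds versions and using only bleeds in the first 12 months. The separation matters because three bleeds that include traumatic ones fail the all-bleeds version but not necessarily the spontaneous-only one.

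1. The number of excluded joints by reason (early end of dosing, joint surgery), and how many already had 3 or more bleeds before exclusion.
2. The percentage with those known failures counted as not resolved, together with worst-case and best-case bounds in which joints with 2 or fewer bleeds and follow-up cut short are counted as all not resolved and then all resolved.
3. A Kaplan-Meier estimate of 12-month freedom from a third bleed, censoring at joint surgery or end of dosing.

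Apply the known-failure count and the bounds to the per-participant percentage too. Because that endpoint needs only one resolved joint, a child is a known failure only when every one of his target joints has reached a third bleed.

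The cost is SAP wording and a few derivations from bleed data already collected. The joint-health figure may look less favourable. The known-failures percentage leans slightly low if exclusion is administrative, and the Kaplan-Meier estimate leans high if exclusion tracks bleeding rate, so they should be read together and with the bounds.
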